Left main disease is a significant lesion in the left main coronary artery of at least 50% diameter stenosis. A protected left main artery means left main with a functioning graft, either venous or arterial, placed to any of the branches of the left main. This is usually the LAD or CX, but could also include one of the branches of those vessels. Having a stent in the left main coronary artery does not in itself constitute a protected left main.

Subject eligibility clarifications:

- Subjects with unprotected left main coronary artery disease may not be enrolled.
- Subjects with protected left main coronary artery disease are eligible for enrollment.

Left Ventricular Ejection Fraction

LVEF is an assessment of the amount of blood emptied from the left ventricle during systolic contraction, which is indicative of global ventricular function.

Lesion Characteristics (ACC/AHA classification)

- Type A lesions: Minimally complex, length <10 mm, concentric, readily accessible, non-angulated segment (<45°), smooth contour, little or no calcification, less than totally occlusive, not ostial in location, no major side branch involvement, and an absence of thrombus.
- Type B lesions: Moderately complex, tubular (length 10 to 20 mm), eccentric, moderate tortuosity of proximal segment, moderately angulated segment (>45°, <90°), irregular contour, moderate or heavy calcification, total occlusions <3 months old, ostial in location, bifurcation lesions requiring double guidewire, and some thrombus present.
- Type C lesions: Severely complex, diffuse (length ≥20 mm), excessive tortuosity of proximal segment, extremely angulated segments >90°, total occlusions >3 months old and/or bridging collaterals, inability to protect major side branches, and degenerated vein grafts with friable lesions.

Refractory chronic total occlusion (CTO) lesion

the CTO lesion that cannot be crossed with conventional guidewires, which shall have any of the following situations:

- previous failed attempt to cross lesion within the past 12 months
- failed attempt to cross CTO with an antegrade guidewire for 10 - 15 minutes of fluoroscopy time
- attempt to cross CTO with an antegrade guidewire resulting in a subintimal wire position

Lesion Length

Lesion length is measured as distance from the proximal to the distal shoulder in the view that demonstrates the stenosis in its most elongated projection. Lesion length is classified as discrete (<10 mm), tubular (10-20 mm), or diffuse (>20 mm).

Lesion Location

Lesion location is the location of the lesion according to the specific coronary artery (i.e., left main, LAD, LCX, or RCA) or bypass graft, and is specified as proximal, mid, or distal. A standard map will be provided to be used for location descriptions.

Leukopenia

Leukopenia is a leukocyte count of $<3.0 \times 10^9/\text{liter}$ for more than 3 days.

Malfunction

A malfunction is a failure of the device to meet performance specifications or otherwise perform as intended.

Myocardial Infarction

The definition of myocardial infarction in FAST-CTO China clinical trial:

Spontaneous myocardial infarction²⁵ (> 72 hours post procedure):

Detection of rise and/or fall of cardiac biomarkers (CK-MB or troponin) with at least one value above the 99th percentile of the upper reference limit (URL) together with evidence of myocardial ischemia with at least one of the following:

- Symptoms of ischemia;
- ECG changes indicative of new ischemia (new ST-T changes or new left bundle branch block [LBBB]);
- Development of pathological Q waves in the ECG;
- Imaging evidence of new loss of viable myocardium or new regional wall motion abnormality.

Percutaneous Coronary Intervention (PCI) and Coronary Artery Bypass Graft (CABG) related Myocardial infarction ²⁶ (≤ 72 hours post procedure)

1. CK-MB in patients with normal baseline concentration reaches any of the following criteria:

- An increase in CK-MB peak to $\geq 10X$ URL during the first 48 hours following the procedure
- An increase in CK-MB peak to $\geq 5X$ URL during the first 48 hours following the procedure, plus new pathological Q-wave in at least 2 contiguous leads, or new persistent LBBB

Or meets any of the following criteria if CK-MB levels are unavailable and baseline troponin concentrations are normal:

- An increase of troponin (I or T) to $\geq 70X$ URL during the first 48 hours following PCI
- An increase of troponin (I or T) to $\geq 35X$ URL during the first 48 hours following PCI, and development of new pathological Q-wave in at least 2 contiguous leads or new persistent LBBB

2. In patient with elevated baseline CK-MB (or troponin) in whom the biomarker levels have shown the tendency to be stable or decrease, if the CK-MB (or troponin) rises by an absolute increment equal to those levels recommended above from the most recent pre-procedure level.

3. In patient with elevated baseline CK-MB (or troponin) in whom the biomarker levels have not shown to be stable or decrease, if the CK-MB (or troponin) rises by an absolute increment equal to those levels recommended above from the most recent pre-procedure level, plus new ST-segment elevation or depression and clinical symptoms related to myocardial infarction, such as new or aggravated heart failure or persistent hypotension.

New York Heart Association classification

- Class I: Patients with no limitation of activities; they suffer no symptoms from ordinary activities
- Class II: Patients with slight, mild limitation of activity; they are comfortable with rest or with mild exertion
- Class III: Patients with marked limitation of activity; they are comfortable at rest
- Class IV: Patients who should be at complete rest, confined to bed or chair; any physical activity brings on discomfort and symptoms occur at rest

Perforation

Perforations are classified as follows:

- Angiographic perforation: Perforation detected by clinical site or Angiographic Core Laboratory at any point during the procedure.

- Clinical perforation: Perforation requiring additional treatment, including efforts to seal the perforation or pericardial drainage, or resulting in significant pericardial effusion, abrupt closure, MI, or death.
- Pericardial hemorrhage/tamponade: Perforation causing tamponade.

Prolonged Angina Pectoris

Prolonged angina pectoris is angina lasting longer than 1 hour.

Pseudoaneurysm

A pseudoaneurysm is an encapsulated hematoma in communication with an artery. It is often difficult to distinguish from an expanding hematoma at the site of arterial puncture. It usually requires surgical repair.

Randomization

Randomization is the procedure by which subjects are assigned to a treatment group based on appropriate theories of probability including those involving random chance and conditional assignments.

Reference Diameter of Normal Arterial Segment

Reference diameter of the normal artery segment is an angiographic measurement of the artery proximal and/or distal to the lesion intended for angioplasty. This is also referred to as “reference vessel diameter” (RVD).

Repeated Intervention

Repeat intervention is a PCI or CABG performed after the end of the index procedure. The repeat intervention should be performed to improve blood flow.

Restenosis Lesion

A restenosed lesion is a previously treated lesion that again has a stenosis.

Restenosis

See Binary Restenosis.

Severe Adverse Device Effect (*Reference: ISO 14155-2011, MEDDEV 2.7/3 12/2010*)

Adverse device effect that has resulted in any of the consequences characteristic of a SAE.

Severe Adverse Event (*Reference: ISO 14155-2011, MEDDEV 2.7/3 12/2010*)

An adverse event that causes the following situations:

Adverse event that:

- Led to death
- Led to a serious deterioration in the health of the subject that either resulted in:
 - A life-threatening illness or injury, or
 - A permanent impairment of a body structure or a body function, or
 - In-patient or prolonged hospitalization of existing hospitalization, or
 - Medical or surgical intervention to prevent life-threatening illness or injury or permanent impairment to body structure or a body function
- Led to fetal distress fetal death or a congenital abnormality or birth defect

Stent Thrombosis (*Reference: the definition of Academic Research Consortium*) (44)

Stent thrombosis should be reported as a cumulative value at the different time points and with the different separate time points. Time 0 is defined as the time point after the guide catheter has been removed and the patient left the catheterization lab.

Timing:

- Acute stent thrombosis*: 0-24 hours after stent implantation
- Subacute stent thrombosis*: >24 hours to 30 days after stent implantation
- Late stent thrombosis: >30 days to 1 year after stent implantation
- Very late stent thrombosis: >1 year after stent implantation

* Acute/subacute can also be replaced by early stent thrombosis. Early stent thrombosis is 0-30 days.

Stent thrombosis may be defined as:

- Confirmed/definite
- Probable
- Possible

Confirmed/Definite (is considered *either* angiographic confirmed or pathologic confirmed)

Angiographic confirmed stent thrombosis is considered to have occurred if:

- TIMI flow is:
 - TIMI flow grade 0 with occlusion originating in the stent or in the segment 5mm proximal or distal to the stent region in the presence of thrombus*
 - TIMI flow grade 1, 2 or 3 originating in the stent or in the segment 5mm proximal or distal to the stent region in the presence of a thrombus*

AND at least one of the following criteria, up to 48 hours, has been fulfilled:

- New onset of ischemic symptoms at rest (typical chest pain with duration >20 minutes)
- New ischemic ECG changes suggestive of acute ischemia
- Typical rise and fall in cardiac biomarkers ($>2\times$ ULN of CK)

The incidental angiographic documentation of stent occlusion in the absence of clinical syndromes is not considered a confirmed stent thrombosis (silent thrombosis).

* Intracoronary thrombus

Non-occlusive thrombus: Spheric, ovoid or irregular non-calcified filling defect or lucency surrounded by contrast material (on 3 sides of within a coronary stenosis) seen in multiple projections, or persistence of contrast material within the lumen, or a visible embolization of intraluminal material downstream.

Occlusive thrombus: A TIMI 0 or TIMI 1 intra-stent or proximal to a stent up to the most adjacent proximal side branch or main branch (if originating from the side branch).

Probable

Clinical definition of probable stent thrombosis is considered to have occurred in the following cases:

- Any unexplained death within the first 30 days
- Irrespective of the time after the index procedure and MI in the absence of any obvious cause which is related to documented acute ischemia in the territory of the implanted stent without angiographic confirmation of stent thrombosis

Possible

Clinical definition of possible stent thrombosis is considered to have occurred with any unexplained death beyond 30 days.

Stroke / Cerebrovascular Accident

An acute symptomatic episode of neurological dysfunction attributed to a vascular cause lasting more than 24 hours or lasting 24 hours or less with a brain imaging study or autopsy showing infarction.

Classification:

- Ischemic Stroke: An acute symptomatic episode of focal cerebral, spinal, or retinal dysfunction caused by an infarction of central nervous system tissue.
- Hemorrhagic Stroke: An acute symptomatic episode of focal or global cerebral or spinal dysfunction caused by a nontraumatic intraparenchymal, intraventricular, or subarachnoid hemorrhage.
- Undetermined Stroke: A stroke with insufficient information to allow categorization as ischemic or hemorrhagic.

An event that lasts < 24 hours may be adjudicated as a stroke if the following treatments were used:

- Pharmacologic, i. e., thrombolytic drug administration, or
- Non-pharmacologic, i.e., neurointerventional procedure (*e.g.*, intracranial angioplasty)

Target Lesion

The target lesion is the lesion selected by the Investigator for treatment with a study device. The target lesion should meet the angiographic enrollment criteria. Only 1 target lesion can be treated during the index procedure as described in the enrollment criteria.

Target Lesion Failure (TLF)

Target lesion failure is any ischemia-driven revascularization of the target lesion, MI (Q-wave and non-Q-wave) related to the target vessel, or (cardiac) death. For the purposes of this protocol, if it cannot be determined with certainty whether the MI was related to the target vessel, it will be considered a TLF.

Target Lesion Revascularization (TLR)

Target lesion revascularization is any ischemia-driven repeat percutaneous intervention, to improve blood flow, of the successfully treated target lesion or bypass surgery of the target vessel with a graft distally to the successfully treated target lesion. A TLR will be considered as ischemia-driven if the target lesion diameter stenosis is $\geq 50\%$ by QCA and there is presence of clinical or functional ischemia which cannot be explained by other coronary or graft lesions. Clinical or functional ischemia is any of the following:

- The subject has a positive functional study corresponding to the area served by the target lesion.
- The subject has ischemic ECG changes at rest in a distribution consistent with the target vessel.
- The subject has ischemic symptoms referable to the target lesion.

A TLR will be considered as ischemia-driven if the lesion diameter stenosis is $\geq 70\%$ by QCA even in the absence of clinical or functional ischemia.

Target vessel

The target vessel is any coronary vessel (*e.g.*, left main coronary artery, LAD, LCX, or RCA) containing a target lesion. Side branches of a target vessel such as the LAD are also considered part of the target vessel.

Target vessel failure (TVF)

Target vessel failure is any ischemia-driven revascularization of the target vessel, MI (Q-wave and non-Q-wave) related to the target vessel or (cardiac) death related to the target vessel. For the

purposes of this protocol, if it cannot be determined with certainty whether the MI was related to the target vessel, it will be considered a TVF.

Target Vessel Revascularization (TVR)

Target vessel revascularization is defined as a TLR (see definition above) or a TVR remote (see definition below).

Target Vessel Revascularization Remote

Target vessel revascularization remote is any ischemia-driven repeat percutaneous intervention, to improve blood flow, or bypass surgery of not previously existing lesions diameter stenosis $\geq 50\%$ by QCA in the target vessel, excluding the target lesion. A TVR will be considered ischemia-driven if the target vessel diameter stenosis is $\geq 50\%$ by QCA and any of the following are present:

- The subject has a positive functional study corresponding to the area served by the target vessel.
- The subject has ischemic ECG changes at rest in a distribution consistent with the target vessel.
- The subject has ischemic symptoms referable to the target vessel.

A TVR will also be considered as ischemia-driven if the lesion diameter stenosis is $\geq 70\%$ even in the absence of clinical or functional ischemia.

Technical Success

Technical success is the ability of the BridgePoint Medical System to successfully facilitate placement of a guidewire beyond a CTO lesion in the true vessel lumen/within the collaterals in those cases that were otherwise refractory to treatment with a currently marketed guidewire.

Thrombus (angiography)

Thrombus (angiographic) is discrete, mobile intraluminal filling with defined borders with/without associated contrast straining, classified as either absent or present.

Thrombolysis in the Classification of Myocardial Infarction

- TIMI 0: No perfusion.
- TIMI 1: Penetration with minimal perfusion. Contrast fails to opacify the entire bed distal to the stenosis of the duration of the cine run.
- TIMI 2: Partial perfusion. Contrast opacifies the entire coronary bed distal to the stenosis. However, the rate of entry and/or clearance is slower in the coronary bed distal to the obstruction than in comparable areas not perfused by the dilated vessel.
- TIMI 3: Complete perfusion. Filling and clearance of contrast equally rapid in the coronary bed distal to stenosis as in other coronary beds.

Total Occlusion

A total occlusion is a lesion with no flow (i.e., TIMI flow 0).

Transient Ischemic Attack

A TIA is a focal ischemic neurological deficit of abrupt onset and of presumed vascular etiology that resolves completely within 24 hours of onset.

Unanticipated Adverse Device Effect (*Reference: 21CFR Part 812*)

Any serious adverse effect on health or safety or any life-threatening problem or death caused by, or associated with a device, if that effect, problem, or death was not previously identified in nature, severity, or degree of incidence in the protocol or application (including a supplementary plan or application), or any other unanticipated serious problem associated with a device that relates to the rights, safety, or welfare of subjects.

Unanticipated Severe Adverse Device Effect (Reference: ISO 14155-2011, MEDDEV 2.7/3 12/2110)

A serious adverse device effect which by its nature, incidence, severity, or outcome has not been identified in the current version of the risk analysis report.

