7.1 Primary Study Endpoint

- Technical Success: the ability of the BridgePoint Medical System to successfully facilitate placement of a guidewire beyond a CTO lesion in the true vessel lumen/within the collaterals
- 30-day MACE rate for CTO cases in which the BridgePoint Medical System was used

MACE is defined as the composite of cardiac death, Q-wave and non-Q-wave myocardial infarction, and any ischemia-driven target lesion revascularization. (for MI definition please refer to section 31.2)

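### Under Protocol section 31.2, a subject with normal baseline biomarkers whose first qualifying rise comes after 48 h and up to 72 h meets no MI criterion, which can understate the primary 30-day MACE rate

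*Protocol*

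**What the plan says.** **Which definition applies.** Protocol section 7.1 defines 30-day MACE as cardiac death, Q-wave or non-Q-wave MI, or ischemia-driven TLR, and adds "for MI definition please refer to section 31.2".

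**The two time classes in section 31.2.** Spontaneous MI applies "> 72 hours post procedure". PCI/CABG-related MI applies "≤ 72 hours post procedure".

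**Criteria inside the second class.**
- Item 1, normal baseline: CK-MB at 10 times the limit, or 5 times with a new Q wave or LBBB. Both need a multiple of "URL during the first 48 hours following the procedure". If CK-MB is unavailable, troponin at 70 times, or 35 times with the same ECG findings. Both need a multiple of "URL during the first 48 hours following PCI".
- Item 2, elevated but stable or falling baseline: the marker "rises by an absolute increment equal to those levels recommended above from the most recent pre-procedure level". No time limit of its own is given.
- Item 3, elevated baseline not shown to be stable or falling: the same increment, "plus new ST-segment elevation or depression and clinical symptoms related to myocardial infarction". Again there is no separate time limit.

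**Other places.** Protocol section 12, under the safety endpoint, words the MI component of 30-day MACE as total CK above twice the upper limit of normal with a positive MB result, and sets no time window. SAP section 3.1 repeats the composite without a biomarker definition. Protocol section 27.3 leaves CEC procedures to a charter that is not among the documents.

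**The concern.** The class header promises cover to 72 h, but the normal-baseline criteria inside it stop at 48 h and the next class does not start until 72 h has passed. A definition that divides follow-up into time classes should leave no interval in which an infarction has no applicable rule.

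MI is a component of the primary safety endpoint and of 6- and 12-month MACE, so an event lost here is lost at every time point. The interval also lies in a period when the protocol itself allows for stent-related events: its timing scheme has "Subacute stent thrombosis*: >24 hours to 30 days after stent implantation". Because the study tests no hypothesis, the descriptive MACE rate and its confidence interval are its main safety result, and their meaning depends on a complete event definition.

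**Working it through.** There is no sample-size or power figure to reproduce. Protocol section 11.2 states no hypothesis, and N = 100 is not derived. The check sets the time windows side by side and then gives a scale.

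**Step 1. Windows.** Each infarct is dated by its first qualifying rise, at t hours after the procedure.

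| t (h) | Item 1, normal baseline (t ≤ 48) | Items 2 and 3, elevated baseline (header only, t ≤ 72) | Spontaneous (t > 72) |
|---|---|---|---|
| 47 | yes | yes | no |
| 48 | yes | yes | no |
| 49 | **no** | yes | **no** |
| 60 | **no** | yes | **no** |
| 72 | **no** | yes | **no** |
| 73 | no | no | yes |

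For a normal baseline the uncovered interval is 72 − 48 = 24 h. For an elevated baseline, items 2 and 3 read literally still apply, although it is unclear whether their reference back to the levels above also imports the 48 h limit.

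**Step 2. Effect of one missed event.** At N = 100 one event is 1/100 = 1 percentage point. With assumed counts and exact (Clopper-Pearson) 95% intervals:
- 6/100 = 6.0% (2.2% to 12.6%)
- 5/100 = 5.0% (1.6% to 11.3%)

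**Step 3. How often.** The documents give no rate of MI at 48 to 72 h. Let q be the assumed proportion of subjects with such an event. The expected number is 100q and the chance of at least one is 1 − (1 − q)^100.

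| Assumed q | Expected events | Chance of at least one |
|---|---|---|
| 0.1% | 0.1 | 9.5% |
| 0.25% | 0.25 | 22.1% |
| 0.5% | 0.5 | 39.4% |
| 1% | 1.0 | 63.4% |

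These values of q are assumptions that show a range, not estimates.

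**Step 4. Detection.** Protocol section 11.1 (note g) requires only one enzyme draw, within 1 day of the procedure. A rise at 48 to 72 h would be found mainly in subjects tested because of symptoms.

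**The case against.** A reader might infer that no infarction between 48 and 72 h can count in primary MACE. The documents do not support that, for several reasons.

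- Items 2 and 3 state no 48 h limit, so subjects with an elevated baseline may be covered. That most subjects will have a normal baseline is an inference from exclusion CE1 (acute MI within 1 week), not a stated fact.
- Section 12 gives an untimed CK/MB rule for the same endpoint. A large CK-MB rise at hour 60 would be expected to count under it.
- The most vivid example, a stent occluding at hour 55, may still enter MACE as ischemia-driven TLR if the lesion is treated again, or as cardiac death. A repeat PCI might also restart the 48 h clock, because the criteria do not say index procedure.
- The charter might settle the boundary, so one cannot say that the CEC must reject such an event.

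Nor do the documents support a large effect. That 24 of 72 hours are uncovered is a share of clock time, not of risk. The 6 non-Q-wave MIs among 147 FAST-CTO subjects (Protocol section 4.3.3.3) have no stated timing, and that section does not say that this definition was used. No pass/fail conclusion can change.

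All of this narrows the point, but none of it closes the gap. Section 7.1 designates 31.2, not section 12, and the section 12 rule cannot classify a subject with troponin only, which section 11.1 (note h) permits. TLR may be a weak backstop: FAST-CTO recorded 6 non-Q-wave MIs and no TLR at 30 days. An infarct managed without reintervention, or one from side-branch loss, is the clearer example of a lost event.

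**Conclusion.** The point holds in a limited form. Under the definition that section 7.1 assigns to the primary endpoint, a normal-baseline subject whose first qualifying rise falls after 48 h and up to 72 h has no MI criterion to meet. The event is lost from MACE if there is no ischemia-driven TLR, no cardiac death, and section 31.2 is applied rather than section 12.

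Compared with a definition whose windows meet, the error runs one way only: it lowers the reported rate, by 1 percentage point per lost event at N = 100. The count of such events is unknown and probably small. The conclusion rests on a literal reading of the 48 h limits and on dating the infarct by its first qualifying rise, which section 31.2 does not spell out. It deserves correction because it affects the primary safety endpoint and is cheap to repair, not because a large bias has been shown.

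**What to change.** Before adjudication, reconcile Protocol sections 31.2 and 12 into one MI definition for MACE. Its PCI/CABG-related and spontaneous windows should meet at a single cut-point, 48 h or 72 h, chosen by the sponsor and the CEC. The definition should also state:
- how an infarct is dated;
- whether the time limit applies to items 2 and 3;
- how a procedural enzyme rise that is still falling is handled.

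The last item matters most if 48 h is chosen. The spontaneous rule needs only one value above the 99th percentile plus evidence of ischemia, so a small procedural leak still falling at hour 50 in a subject with chest discomfort could be counted as MI. Extending the item 1 limits to 72 h would also close the gap. Moving the boundary alone would leave the section 12 conflict in place.

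Carry the agreed definition into SAP section 3.1 and the CEC charter. The cost is a protocol amendment with matching edits, and no extra visits, tests or subjects. The downside is a possibly slightly higher reported MACE rate. Settling the definition before events are known avoids any appearance of post hoc adjudication.
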